CR	Complete response
CRF	Case Report/Record Form; the term CRF can be applied to either EDC or Paper
CRO	Contract Research Organization
CSR	Clinical study report
CSR addendum	An addendum to Clinical Study Report (CSR) that captures all the additional information that is not included in the CSR
CT	Computed tomography
DDI	Drug-Drug-Interaction
DFS	Disease-free survival
DLT	Dose Limiting Toxicity
DS&E	Drug Safety and Epidemiology
ECG	Electrocardiogram
ECOG	Eastern cooperative oncology group
ER	Estrogen receptor
FAS	Full Analysis Set
FISH	Fluoreszenz-in-situ-Hybridization
FSH	follikelstimulierendes Hormon
GBM	Glioblastoma multiforme
i.v.	intravenous(ly)
ICH	International Conference on Harmonization
IEC	Independent Ethics Committee
IRB	Institutional Review Board
LPFV	Last Patient First Visit
LPLV	Last Patient Last Visit
MAP	Master Analysis Plan documents project standards in the statistical methods which will be used within the individual clinical trial RAP documentation
MTD	Maximum Tolerated Dose
NCI-CTCAE	National cancer institute – common terminolgy criteria for adverse events
NCRNPD	neither complete response nor progressive disease
PD	Progressive disease
PFS	Progression Free Survival
p.o.	per os/by mouth/orally
PHI	Protected Health Information

PgR	Progesterone receptor
PR	Partial Response
QTcF	QT corrected for HR using Fridericia's method
ORR	Overall response rate
OS	Overall survival
RAP	The Report and Analysis Plan (RAP) is a regulatory document which provides evidence of preplanned analyses
REB	Research Ethics Board
RECIST	Response Evaluation Criteria in Solid Tumors
SAE	Serious Adverse Event
SAF	Safety Analysis Set
SD	Stable disease
SISH	silver-in situ-Hybridisation
SmPC	Summaries of Product Characteristics
SOD	Sum of Diameter
SOP	Standard Operating Procedure
TTF	Time to treatment failure
TPP	Time to Progression
UNK	Unknown

1 Introduction

This statistical analysis plan describes the final and the three pre-planned interim analyses. It is based on the 4th amendment of the study protocol, dated 05-JUN-2019.

1.1 Study design

This was a national, multi-center, open-label, phase IIIb trial to determine the efficacy and safety of treatment with ribociclib (LEE011) plus letrozole in patients with HR+, HER2-negative advanced (recurrent or metastatic) breast cancer.

In this trial a total of 500 patients from 100 centers were planned to be recruited.

The study was designed as an open-label, single-arm trial, hence no randomization took place.

The primary efficacy and safety analysis was conducted on all patient data at the time all patients who are still receiving study drug will have completed at least 24 weeks of treatment (or discontinued prematurely). The additional data for any patients continuing to receive study drug past these times, as allowed by the protocol, was further summarized in a report once these patients completed the study.

Three interim analyses were planned during the study. The first interim analysis was conducted one year after the first patient has been enrolled and included a preliminary analysis on safety. The second interim analysis was conducted 12 months after LPFV in the 30% pretreated and premenopausal cohort (=Cohort B, see section 2.2.1 Subgroup of interest) and included a preliminary analysis on safety, efficacy and quality of life. The third interim analysis took place 6 months after the last patient had been recruited into cohort A (see section 2.2.1 Subgroup of interest) and included a preliminary analysis on safety and efficacy.

1.2 Study objectives and endpoints

Objectives and related endpoints are described in the table below (in accordance with Table 3-1 from the protocol).

Primary Objective	Endpoint

The primary objective of this study is the assessment of the clinical benefit rate after 24 weeks for the total population and for cohorts A and B separately:
 
1. Cohort A: postmenopausal women and men who received no prior treatment for advanced disease. (70% group)2. Cohort B: pre-, and perimenopausal women who received no prior treatment for advanced disease as well as pre-, peri- and postmenopausal women and men who received no more than 1 prior chemotherapy and 2 prior lines of endocrine therapy for advanced disease (30% group)	Clinical Benefit Rate (CBR) after 24 weeks of treatment as defined by RECIST 1.1 as percentage of patients with CR, PR or SD until week 24 or longer as well as patients with NCRNPD >24 weeks for patients with non-measurable disease

Secondary Objectives	Endpoint

To assess the clinical benefit rate (CBR) after 24 weeks among Cohort B1 and B2:
	
Clinical Benefit Rate (CBR) after 24 weeks of treatment as defined by RECIST 1.1 as percentage of patients with CR, PR or SD until week 24 or longer as well as patients with NCRNPD >24 weeks for patients with non-measurable disease

Progression-free survival (PFS) for the three different populations: Cohort A, Cohort B1, Cohort B2
	
PFS based on radiologic assessment by investigator using RECIST 1.1 criteria (e.g. median PFS, PFS rate at 12 and 18 months)

Overall survival (OS) for the three different populations, defined as the time from date of start of treatment to date of death due to any cause.
	
Overall survival (OS) (e.g. OS rate at 12 and 24 months)

Overall response rate (ORR) for the three different populations, defined as complete response or partial response as defined by RECIST 1.1
	
Overall Response Rate (ORR) after 24 weeks

To evaluate the safety and tolerability of ribociclib in combination with letrozole (and goserelin in premenopausal patients)
	
Frequency/severity of AEs AEs of special interest: Frequency, severity, frequency per patient, time to Event, duration of Event and recurrence

To evaluate patient reported outcomes for health related quality of life
	
Laboratory values Time to 10% deterioration in the global health status/QOL scale score of the EORTC QLQ-C30

	
Change from baseline in the global health status/QOL scale score of the EORTC QLQ-C30

Exploratory Objectives (out of scope of this statistical analysis plan)	Endpoint
[REDACTED]	Analysis methods and endpoints will be used that resemble the current scientific standard at the time of analysis.
[REDACTED]	Such analyses will be described in a separate analysis plan
[REDACTED]	
[REDACTED]	

2 Statistical methods

2.1 Data analysis general information

The data were analyzed by [REDACTED]. Analysis was carried out using the SAS (Statistial Analysis System) software, version 9.2, 2009, SAS Institute Inc., Cary, North Carolina, USA.

Interim analyses were carried out by [REDACTED] as well. The analyses were based on definitions within this SAP and RAP 7.1 and the tables generated for the particular interim analyses were marked in RAP 7.2.

The first interim analysis included a preliminary analysis of safety (as well as baseline characteristics). The second interim analysis included a preliminary analysis of safety, efficacy and quality of life. The third interim analysis included a preliminary analysis of safety and efficacy. The primary efficacy and safety analysis was conducted on all patient data at the time all patients who are still receiving study drug had completed at least 24 weeks of treatment (or discontinued prematurely). The additional data for any patients continuing to receive study drug past these times, as allowed by the protocol, were further summarized in a report once these patients completed the study.

In general, categorical variables were summarized by absolute and relative frequencies. Continuous variables were summarized by descriptive statistics (number of non-missing observations, mean, standard deviation, minimum, median and maximum). Time-to-event data including rates of affected patients were assessed using the Kaplan-Meier method. The primary aim of this trial was in estimation rather than significance testing of statistical hypotheses. Thus, mainly statistical estimators along with appropriate two-sided 95% confidence intervals were used. However, changes from baseline were explored using suitable statistical tests for paired samples. No adjustment for multiplicity was done due to the exploratory nature of the trial.

The data from all participating centers were combined, so that an adequate number of patients was available for analysis and the factor center was included in the analysis of the primary endpoint.

2.1.1 General definitions

Study treatment: The combination of drugs including investigational drug ribociclib as well as letrozole and goserelin acetate.

On-treatment period: Period the patient was exposed to any study treatment, i.e from the first administration of any study treatment at or after C1/D1 to the last administration of any study treatment (for ribociclib and letrozole documented on the Treatment Completion CRF and for Goserelin documented on the Dosage Administration record but not later than the End-of-study visit (see 5.2.1)

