2.8 Safety analyses

The analysis of safety objectives was described in section 10.5.2.1. of the study protocol. All listings and tables are presented for the Safety Analysis Set by pretreatment group and total, i.e. cohorts A, B1, B2, B and total:

- postmenopausal women or men without prior treatment for advanced disease (cohort A)
- pre- and perimenopausal women without prior treatment for advanced disease (cohort B1)
- pre-, peri and postmenopausal women with prior treatment for advanced disease (cohort B2)

The overall observation period will be divided into three mutually exclusive segments:

1. pre-treatment period: from day of patient's informed consent to the day before first dose of study treatment
2. on-treatment period plus 30 days: from day of first dose of study medication to 30 days after last dose of study treatment
3. post-treatment period: starting at day 30+1 after last dose of study treatment.

Goserelin and letrozole after end of treatment were not considered as study treatment, see 5.2.1.

As a sensitivity analysis selected analysis tables (see RAP module 7.1) were displayed for a modified SAF population which excludes patients from centers with a relevant inspection finding.

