5.2 Definition of safety variables

5.2.1 Duration of study treatment exposure

For ribociclib and letrozole the duration of exposure (days) = date of last administration of ribociclib resp. letrozole – date of first administration of ribociclib resp. letrozole + 1 day. The first administration of the study treatments ribociclib and letrozole are taken from the respective Dosage Administration Record, i.e. the date of first dose > 0 at/after C1/D1. The date of last administration of the study treatments ribociclib and letrozole are taken from the Treatment Completion CRF. In case of ongoing treatment, resulting in missing end days on Treatment Completion CRF, the end date is substituted hierarchy by:

- End date of last administration with dose >0 of ribociclib resp. letrozole on the Dosage Administration record before End-of-Treatment-visit
- If the end date of the last administration with dose >0 of ribociclib resp. letrozole on the Dosage Administration is missing (normally because “ongoing” is ticked) the date of the last visit during the on-treatment period (C1/D1 to End-of-treatment) is used to substitute the end date.

For goselerin the duration of exposure (days) = date of last administration of goselerin – date of first administration of goselerin + 1 day. The first administration of the study treatment goselerin is taken from the respective Dosage Administration Record, i.e. the first dose > 0 at/after C1/D1. The end of the third component goselerin is not asked at the Treatment Completion CRF and must be derived from the Dosage Administration record therefore. Goselerin may be continued in combination with a follow-up therapy and may be documented on the Dosage Administration Record, although it is no longer a study treatment. For this reason

the date of last goselerin administration is the last dose > 0 administered until the End-of-treatment visit.

The exposure to study treatment is displayed for each of the third components separately, and in combination. For combination, called “exposure to any of the study treatments”, the first start date and the last end date of the study treatments is used for calculation.

The duration of exposure includes the periods of temporary interruption (of any component of the study treatment for any reason).

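### SAP 2.1.1 caps the last goserelin dose at the End-of-study visit, but SAP 5.2.1, which it cites, and SAP 2.8 cut off at end of treatment; coded literally, 2.1.1 lengthens the on-treatment period for goserelin recipients only

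*SAP*

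**What the plan says.** SAP 2.1.1 defines the on-treatment period as running from the first to the last administration of any study treatment. The source of the last date depends on the drug. Ribociclib and letrozole take it from the treatment completion form. Goserelin has its own rule: the date is the one "for Goserelin documented on the Dosage Administration record but not later than the End-of-study visit". The definition then refers the reader to 5.2.1.

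SAP 5.2.1, the section cited, sets a different limit: "the date of last goselerin administration is the last dose > 0 administered until the End-of-treatment visit". It gives its reason. "Goselerin may be continued in combination with a follow-up therapy", and such doses "may be documented on the Dosage Administration Record, although it is no longer a study treatment".

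SAP 2.8 repeats the exclusion for the safety analyses: "Goserelin and letrozole after end of treatment were not considered as study treatment, see 5.2.1". The same section sets the safety segment as first dose to 30 days after the last dose of study treatment. SAP 5.2.1 also describes the on-treatment visits in a way that fits its own limit: "the date of the last visit during the on-treatment period (C1/D1 to End-of-treatment) is used" when an end date is missing. SAP 5.4.5 uses the same visit range.

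**The concern.** End of treatment and end of study are different points in this trial. Protocol 7.1.3 says that the end-of-treatment or premature-withdrawal visit is not the end of the study. Protocol 7.1.4 and 7.1.5 continue tumour and survival follow-up after treatment stops. A goserelin date limited by the one visit can therefore differ from a goserelin date limited by the other.

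The later limit is attached to goserelin alone. Ribociclib and letrozole end dates come from a form that records the end of study treatment. Goserelin is read from the dosing record, on which the SAP itself expects doses given with a subsequent therapy.

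Section 2.1.1 is the SAP's general definition of the term, and later sections use it: the treatment-emergent window (2.8.1), the count of events of special interest per patient (2.8.1.1), deaths by period (2.8.2) and the number of on-treatment visits (2.3.1). Results are shown in separate columns for cohorts A, B, B1 and B2. An over-long period would fall mainly in the columns that hold pre- and perimenopausal women. Deaths are the most exposed, because protocol 7.1.5 collects survival status whatever the reason for stopping treatment.

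**Working it through.** The plan gives no figure for this point, so the check is a comparison of the definitions, followed by an illustration.

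**Cut-off for the last goserelin dose, by section**

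| Section | Latest goserelin dose counted, or on-treatment range |
|---|---|
| SAP 2.1.1 | up to the End-of-study visit, with a reference to 5.2.1 |
| SAP 5.2.1 | up to the End-of-treatment visit |
| SAP 2.8 | goserelin after end of treatment is not study treatment |
| SAP 5.4.5 | on-treatment visits run from C1/D1 to the End-of-treatment visit |

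Section 2.1.1 is the only one of the four with the later limit, and the section it cites contradicts it.

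**Which outputs depend on which section**

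- Exposure: SAP 2.4.1 refers to 5.2.1 for the duration. Section 5.2.1 builds the combined exposure from the first start date and last end date of the components, with goserelin limited at End of treatment.
- Dose intensity: SAP 5.2.3 divides cumulative dose by that exposure. The 2.1.1 date does not enter.
- Treatment-emergent events and deaths by period: both use the on-treatment period plus 30 days. Section 2.8 gives the window and excludes later goserelin, but the term itself is defined in 2.1.1. This is where a literal reading of 2.1.1 could take effect.

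**Illustration**

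Inputs: goserelin on day 1 of each 28-day cycle (protocol Table 6-1); a 30-day addition after the last dose (SAP 2.8). Assumptions: all study drugs have their last on-treatment dose on day 0, and the patient then has k further goserelin doses at 28-day intervals on the dosing record. The end-of-treatment visit is due within 7 days of stopping (protocol 7.1.3), so every further dose falls after it.

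- End of window under 5.2.1 and 2.8: 0 + 30 = day 30.
- End of window under literal 2.1.1: 28k + 30.
  - k = 1: 28 + 30 = day 58
  - k = 6: 168 + 30 = day 198
- Difference: 28k, which is 28 days for k = 1 and 168 days for k = 6.
- Patient without goserelin: day 30 under either rule.

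The range of k is assumed. The documents give neither the number of patients who continued goserelin nor the duration.

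**The case against.** The strongest reply is that the SAP already resolves the matter. Section 2.1.1 speaks of study treatment and points to 5.2.1, and both 5.2.1 and 2.8 say that goserelin after end of treatment is not study treatment. A programmer who follows the reference reaches the End-of-treatment limit. This stands as a limit on the consequence: nothing shows that later follow-up is in fact counted as on-treatment. It does not remove the contradiction, because 2.1.1 states its own, different limit in the general definition.

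Several stronger readings are tempting and are not supported.

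- A reader might infer that ribociclib dose intensity is diluted in goserelin recipients. It is not under the SAP as written, since exposure and its use as a denominator come from 5.2.1.
- A reader might set the 5.5-month median PFS of the pretreated phase Ib group (protocol 1.2.6) against the 80-week treatment horizon and infer a gap of more than a year. The phase Ib patients had to be postmenopausal, so they do not represent the women given goserelin here. The 80 weeks is a study-level end of treatment counted from the last patient, not one patient's interval to an End-of-study visit. Protocol 4.3 also speaks of 30 days of safety follow-up after the individual's last dose to reach the end of study. On that reading only one further 28-day dose fits, which is the k = 1 case.
- A reader might infer broad inflation of adverse event counts. Protocol 4.1 and 6.6 ask for events beyond the 30-day interval only when causality is suspected. The special-interest counts in 2.8.1.1 are of treatment-emergent events, so the window in 2.8 already bounds them.
- A reader might infer that cohort A is untouched and the comparison with it distorted. Protocol 6.1 allows men to receive goserelin, so some cohort A men could be affected, and the cohort columns are descriptive.

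**Conclusion.** The inconsistency is real and lies in operative text. SAP 2.1.1 is wrong as written when set against the section it cites and against 2.8 and 5.4.5. The harm is conditional: it arises only if the on-treatment end date is coded from 2.1.1 alone. In that case the period is too long for goserelin recipients only. The classification of deaths by period is the output most exposed, followed by late adverse events suspected to be related.

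The size cannot be determined from the documents. The shift of 28 to 168 days rests on the assumed 1 to 6 further doses and on those doses being on the dosing record. Exposure and dose intensity are unaffected. So is the primary endpoint, which SAP 2.5.1 derives from tumour assessments to week 24 without using this period.

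**What to change.** In SAP 2.1.1, replace the term End-of-study visit with End-of-treatment visit, so that the analysis cut-off for goserelin matches 5.2.1 and 2.8. Add one sentence saying that this single last-dose date is used for treatment-emergent adverse events and for deaths by period. Because much of the SAP is written in the past tense and describes interim analyses as done, also confirm which cut-off was programmed. If it was the later one, rerun the affected safety tables.

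The text change is one term and one sentence. It needs no new data and changes no clinical procedure. Confirming the code is a short check.

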2.2 Analysis sets

The **Enrolled Patient Population (ENR)** includes all patients who signed an informed consent regardless whether they received study treatment or not.

The **Full Analysis Set (FAS)** comprises all patients to whom study treatment has been assigned. Patients with critical findings by an inspection were excluded.

The **Safety Set (SAF)** includes all patients who received at least one dose of study treatment.

The **Per-Protocol Set (PPS)** consists of a subset of the patients in the FAS who are compliant with requirements of the CSP. During the data review meeting the violations against the CSP were identified and assessed as relevant for analysis (called “major”) or not (“minor”). The PPS may be analyzed if a substantial number of patients was not compliant with the requirements of CSP. This decision will be done during a data review meeting before analysis.

2.2.1 Subgroup of interest

All results of this study were displayed for the total population and for cohorts A, B, B1 and B2 separately (each cohort is displayed in a separate column):

- **Cohort A:** Postmenopausal women and men who received no prior treatment for advanced disease.
- **Cohort B:** Pre-, and perimenopausal women who received no prior treatment for advanced disease (**B1**) as well as pre-, peri- and postmenopausal women and men who received prior therapy (**B2**). According to exclusion criteria only patients with no more than 1 prior chemotherapy and 2 prior lines of endocrine therapy for advanced disease were included.

Cohorts:	Postmenopausal women or men	Pre- or perimenopausal women
Treatment naive	A	B1
Pre-treated	B2	B2

Further subgroups of interest may be analyzed for selected endpoints. These subgroups were:

- Men
- Pre- and perimenopausal women

across all cohorts.

During review of analysis tables it will be defined which tables will be additionally produced for the further subgroups.

2.3 Patient disposition, demographics and other baseline characteristics

Demographic and other baseline characteristics were summarized for the Full Analysis Set (FAS). Baseline characteristics include prior medication, past/current medical conditions and disease history.

2.3.1 Patient disposition

Patient disposition was summarized for all patients by absolute and relative frequency of patients completing the study phases screening, treatment and study completion. Reasons for discontinuation were shown for the Enrolled Patient Population (ENR) for screening resp. the Full Analysis Set (FAS).

The number of patients per visit and the number of on-treatment visits were given for the FAS.

Frequencies of major (=leading to exclusion from per-protocol population) and minor protocol violations were reported.

2.4 Treatments (study treatment, rescue medication, concomitant therapies, compliance)

2.4.1 Study treatment / compliance

Duration (days) of study treatment exposure for patients who took at least one dose of any of the components of the study treatment was calculated as the difference between the last and first day of drug application +1 day. For details see 5.2.1.

The duration includes the periods of temporary interruptions for any reason. Additionally, duration of drug exposure was summarized using descriptive statistics separately for ribociclib, letrozole and goserelin, respectively.

The cumulative dose, dose intensity (DI) and relative dose intensity (RDI) were summarized by cohort. Cumulative dose is defined as the total dose given during the study treatment exposure. For patients who did not receive the respective drug the cumulative dose was set to zero (in case of goselerin for pre- and perimenopausal patients only). The dose intensity (DI) for patients with non-zero duration of exposure is defined as cumulative dose / duration of exposure. For patients who did not receive any drug, the DI was set to zero. Planned dose intensity (PDI) is the assigned dose in mg/day prescribed by the investigator to be given to patients. Relative dose intensity (RDI) is defined as DI divided by PDI. The DI and RDI were summarized separately for each of the study treatment components, but using the duration of the whole study treatment exposure, not the duration of each of the components. In addition, for combinations, the RDI was calculated as mean RDI of each of the study treatment components on a per-patient basis.

Ribociclib interruptions (defined as null doses for any reason except “as per protocol”) were displayed by the number of affected patients, the total duration and frequencies of study drug interruptions. The total duration was calculated by end date – start date of interruption (for any reason except “as per-protocol”) + 1 day. All interruptions of a patient are summed up to the total duration (for any reason except “as per protocol”)

Frequencies of the number of patients with ribociclib dose reduction (defined as dose > 0 mg but lower than the previous dose) as well as the number of dose reductions by reason were given. Additionally, dose reductions and dose interruptions were tabulated in combined fashion. In the combined summary, the dose interruptions were considered as dose reductions to 0 mg and therefore all reductions/interruptions were labeled as reductions and tabulated in one table.

These analyses were performed for the Safety Set (SAF).

